4.3.2.9 Quality of Life Assessments

The impact of OIT on participants' health-related quality of life (HRQL) will be assessed both from parents' and participants' perspective using disease-specific validated "food-allergy quality of life questionnaire" (FAQL-Q) in its parental, child and teenager forms. The FAQLQ-PF (parent form) will be administered to all parents; FAQLQ-CF (child form) administered to patients age 8-12 years at commencement of study; FAQLQ-TF (teenager form) administered to patients age 13-18 years at commencement of study. To ensure the ability to compare responses consistently during the 12 months of OIT, children who are age 12 at study commencement will be asked to complete the Teenage version unless there are difficulties with comprehension which preclude this.

These will be performed for subjects in the active arm at the following points during the study:

- i. baseline, at screening (TS).
- ii. prior to cookie initial escalation (T1C).
- iii. prior to pancake initial escalation (T1P/ T2P)
- iv. prior to the DS FC (T3).
- v. prior to SU FC (T4).

Subjects in the control arm will be assessed at baseline (TS) and prior to DS FC (T3).

4.3.2.10 Laboratory Assessments

The development of tolerance in immunotherapy is associated with several immunological changes, including decreases in egg-specific IgE levels with concomitant increases in IgG4 levels. Serum IgE to egg white, ovomucoid and ovalbumin will be performed at baseline screening (TS) and at the end of study (T3) for all subjects and additionally for active subjects who have a visit at T4.

Other than serum immunoglobins assay, 3 mL of Ethylenediaminetetraacetic acid anti-coagulated blood will be concurrently collected (TS, T3 and if applicable, T4) and sent to a core laboratory for peripheral blood mononuclear (PBMC) preparation. We expect 3 mL of blood to yield approximately 6 million PBMCs. These following experiments will be performed:

- i. DNA-human leukocyte antigen (HLA) genotypes: DNA will be isolated from 0.2 mL of blood to perform HLA typing to determine the appropriate candidates for major histocompatibility complex (MHC) tetramers analysis and genome sequencing if new data arises that indicates the importance of other non-HLA genetic variants for allergy manifestation.
- ii. Multi-parametric immune cell profiling: We will utilise multi-parametric cytometry to holistically characterise the immune system and determine the differences between non-responders and those with SU to identify immune signatures that confer resistance to OIT. Absolute counts of B, T, natural killer and dendritic cell subsets will be characterised.

- iii. Transcriptomic analysis: This will be done either at the immune cell subset or single cell level depending on the immune cell profiling data to identify the pathways responsible for the differences in response to OIT.
- iv. Multi-parametric cytokines/chemokines profiling: This will be done on the plasma stored after PBMC preparation if the cytometry data indicates the involvement of specific cytokines/chemokines in allergy manifestation.

4.3.3 Final Study Visit:

The final study visit will be on the day of DS challenge (T3) for controls and for active subjects who did not achieve desensitisation. The final study visit will be on the day of SU challenge (T4) for those successfully desensitised at T3.

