2.3 Secondary Objectives

1. To evaluate the efficacy of pancake OIT in inducing sustained unresponsiveness in egg-allergic children.
2. To evaluate the safety and feasibility of using pancake as OIT for egg-allergic children.
3. To compare immunological outcomes (skin prick test to egg white, serum IgE to egg white, ovomucoid, ovalbumin) at baseline and end of OIT program.
4. To assess the impact of OIT on health-related quality of life.
5. To compare the immune cell profiles at baseline and end of OIT program.
6. To identify the mechanistic basis of resistance, desensitisation and SU to OIT.

2.4 Potential Risks and Benefits:

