3 STUDY POPULATION

3.1 List The Number and Nature of Subjects to be Enrolled.

Children aged 2-15 years with current egg allergy will be identified from the KKH Paediatric Allergy Service. A total of 33 egg-allergic patients will be recruited and randomised 2:1 to active (n=22) or control (n=11) groups.

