4.3.2.7 Sustained Unresponsiveness (SU) Food Challenge (T4)

Desensitised subjects in the active arm (tolerating 4443mg of cooked egg at T3) will be asked to stop OIT and all baked egg products (if they had been taking them) for approximately 6-8 weeks prior to returning for a repeat FC to assess for sustained unresponsiveness. The dosing protocol for SU FC will be the same as that of DS FC (Table 7).

Participants who tolerate 4443mg of cooked egg at SU FC will be allowed ad libitum cooked egg consumption post study. Participants who develop allergic reactions at SU FC will resume previous maintenance dose.

4.3.2.8 Clinical assessment and procedures during open FC (screening FC, baked egg FC, DS FC, SU FC)

All challenges will be conducted in the Allergy outpatient unit, with staff fully trained in the management of allergic reactions including anaphylaxis. Emergency equipment (including oxygen and suction) and medication will be checked beforehand, as per local protocol and international criteria for performance of FC.

All subjects will be assessed prior to FC to determine suitability for a challenge, as follows:

- No intercurrent illness
- No exacerbation in allergic symptoms (eczema, asthma, food allergy) in the preceding week.
- No short-acting β 2 agonists used in the past 12 hours
- No recent antihistamine exposure (e.g. cetirizine, loratadine) in the past 48 hours (72 hours for fexofenadine, 5 days for long-acting antihistamine (e.g. chlorphenamine, desloratadine).

- No oral steroids have been taken in the past 2 weeks
- Baseline observations (temperature, blood pressure, heart and respiratory rate, oxygen saturations,) within the normal range.
- Baseline physical examination must not reveal any significant acute findings.

The clinical team may elect to secure intravenous access by cannulation as an additional safety precaution at challenge. This will allow treatment to be easily and rapidly administered in the event of a significant allergic reaction, and also allows blood to be collected without further venepuncture.

Participants will be monitored including heart rate, blood pressure and oxygen saturations. Clinical manifestations will be assessed throughout the challenge.

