5.2 Storage and Drug Accountability

Storage Requirements and Stability (Temperature, Duration)

Shelf Stable Ingredients

	Shelf (unopened)	Shelf (opened)
Plain flour	Use by date	6 months*
Sugar	Use by date	18 – 24 months
Oil	Use by date	3 – 5 months
Baking powder	Use by date	3 – 6 months

* Opened flour packets should be stored in air-tight containers.

Perishable ingredients

	Refrigerator
Eggs, in shell	3 – 5 weeks OR Use by date
Butter/ Milk-free margarine	1 – 2 months 6 months
Fresh cow's milk	Use by date (unopened) 3 days (opened)

Baked Products

	Room Temperature (~25°C)	Refrigerator (0 – 4°C)	Freezer
Cookies	2-3 weeks	2 months	8-12 months
Pancakes	2 hours	2 – 3 days	2 months

- Pancake batter must be cooked within 2 hours upon preparation.
- General safe food preparation and handling practices apply.

6 TREATMENT**6.1 Rationale for Selection of Dose**

Current OIT regimens typically involve the daily consumption of an allergen, commencing at a very low dose followed by dose increments over several hours during initial escalation phase and periodically (usually every 2-4 weeks) during build-up phase until the target maintenance dose is achieved (12) This maintenance dose is then continued on a daily basis for months to years. There is considerable variation between studies regarding starting and target maintenance doses.

Egg OIT (using eggs in various forms such as lyophilized egg, dehydrated egg white, pasteurized raw egg white, lightly cooked eggs or hard-boiled eggs) has been reported with much heterogeneity in desensitisation rates ranging from 55% to 100%. Furthermore, the ability of current protocols to induce SU appear to be even more limited (~30%). It is possible that longer duration and higher doses of treatment resulting in higher cumulative dose of allergen may lead to higher rates of allergy remission but this would have to be balanced against the risk of allergic reactions. Safety of egg OIT, just like other OIT, is a concern with early discontinuation due to adverse events reported in 12.5%-36% of children (13).

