9 SAMPLE SIZE AND STATISTICAL METHODS

9.1 Determination of Sample Size

The incidence of natural resolution of egg allergy over 12 month period is about 15% (4),(10). The efficacy for desensitisation using raw/cooked eggs is about 80% (ranging between 55% -100%) whilst that for OIT using baked egg products is about 50%. As there are no prior studies using pancake to desensitise egg-allergic patients, we are estimating the efficacy to be in between that of raw/cooked eggs and baked eggs, at about 65%. We plan to recruit 33 egg-allergic children to the study, who will be randomised 2:1 to active (n=22) or control (n=11) groups. This will allow us to detect a difference in rates of desensitisation of 50%, with 80% power using a two-sided significance level of 0.05, whilst allowing for a 30% attrition rate. Sample size calculation was performed using PASS 14 (Power Analysis and Sample Size Software (2015). NCSS, LLC. Kaysville, Utah, USA, [ncss.com/software/pass.](http://ncss.com/software/pass/)).

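### The immune-profiling plan contrasts only non-responders with SU children and calls any difference resistance; children desensitised without SU enter no stated comparison, so the two steps of response cannot be told apart

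*Combined protocol and SAP*

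**What the plan says.** Secondary objective 6 (section 2.3) is "To identify the mechanistic basis of resistance, desensitisation and SU to OIT", which names three states. Section 1.1 defines desensitisation and SU separately.

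The design produces an intermediate group. Active children who pass the cooked-egg challenge at T3 stop OIT for about 6-8 weeks and are challenged again at T4. Section 4.3.2.7 foresees that some will fail: "Participants who develop allergic reactions at SU FC will resume previous maintenance dose".

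Section 4.3.2.10 collects blood for immune profiling at TS, at T3 and, where it applies, at T4. Item ii names the only contrast between response groups, which is to "determine the differences between non-responders and those with SU to identify immune signatures that confer resistance to OIT". Item iii (transcriptomics) refers only in general terms to pathways behind differing responses. Section 9.2.2 plans paired before-and-after tests of immunological outcomes within each group, with no test between response groups. The term non-responder is not defined.

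**The concern.** A non-responder has not become desensitised. An SU child has become desensitised and has also stayed so after stopping. A difference between these two extremes may belong to either step, and the contrast cannot say which. Item ii nevertheless assigns every such difference to resistance.

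The children who could separate the two steps are those who pass T3 and fail T4. If they resemble SU children on a marker, the marker goes with becoming desensitised. If they resemble non-responders, it goes with sustaining the response. Their blood is already being collected, but no section gives them a place in a comparison.

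Two things are at stake. A marker of sustained response could be published as a mechanism of OIT resistance. And a true resistance marker would be tested against only some of the desensitised children available.

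**Working it through.** **The plan's own figure.** The documents give no sample size or power for this contrast. The only stated calculation is for the primary endpoint (section 9.1: 65% v 15%, 33 children, 80% power, 30% attrition). With about 15 v 8 completers, an unpooled z test has SE = √(0.65×0.35/15 + 0.15×0.85/8) = 0.176, and 0.50/0.176 − 1.96 = 0.875, so power is 80.9%. It reproduces on that formula but does not bear on this point.

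**Inputs from the documents.** "A total of 33 egg-allergic patients will be recruited and randomised 2:1 to active (n=22) or control (n=11) groups" (section 3.1). Desensitisation 65% (section 9.1). SU 28-50% (section 1.1), or about 30% (section 6.1).

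**Assumed, because the documents give nothing.** One normally distributed marker with unit variance; shift d = 1.0 or 1.5 SD; two-sided t test at 0.05; no multiplicity correction; SU rate applied to all 22 active children; a non-responder is any active child not desensitised.

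**Group sizes.** Non-responders 22×0.35 = 7.7, about 8. Desensitised 22×0.65 = 14.3, about 14. SU 22×0.28 = 6.2, about 6, up to 22×0.50 = 11. This leaves 8 down to 3 children desensitised without SU, so the groups run from 8/8/6 to 8/3/11 (non-responder / desensitised only / SU).

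**True resistance marker (both desensitised groups shifted by d).** Power comes from the noncentral t distribution with ncp = d/√(1/n₁ + 1/n₂).
- 8 v 6: ncp = 1.85 or 2.78; power 40% or 72%.
- 8 v 11: ncp = 2.15 or 3.23; power 53% or 86%.
- 8 v 14 (all T3 passers): ncp = 2.26 or 3.38; power 57% or 90%.

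**SU-only marker (only SU children shifted by d).** Among all T3 passers the mean shift is diluted to d×6/14 = 0.43d at 8/8/6, and to d×11/14 = 0.79d at 8/3/11. Share of simulated trials that are significant:

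| Contrast | 8/8/6, d = 1.0 / 1.5 | 8/3/11, d = 1.0 / 1.5 |
|---|---|---|
| Non-responder v SU (planned) | 40% / 72% | 53% / 86% |
| Non-responder v all T3 passers | 12% / 18% | 35% / 62% |
| Non-responder v desensitised only | about 5% | about 5% |
| SU v desensitised only | 40% / 72% | 29% / 56% |

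The first row is the rate at which a sustained-response marker would be reported as resistance. The last row is the rate at which it would be found under its proper label. With SU at 30% rounded to 8/7/7, the first two rows are 43% / 76% and 15% / 25%.

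**Graded marker (desensitised-only children midway).** At 8/8/6 the planned contrast has 40% / 72% power and the all-passer contrast 32% / 60%. At 8/3/11 it is 53% / 86% against 48% / 80%.

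**Sensitivity.** With the plan's 30% attrition, 22×0.7 = 15.4, about 15 completers (5/6/4): power for a resistance marker is 25% / 49% as planned against 39% / 72% with all T3 passers. If the SU rate applies only to the 14 desensitised children, 30% gives about 4 SU children, and power is 32% / 60% against 57% / 90%.

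**The case against.** **Comparing extremes is a recognised discovery strategy.** For a graded marker the planned contrast has more power than pooling all T3 passers, by 8 to 12 points at 8/8/6, and the documents do not say which marker shape is likelier. This stands. It is a reason to keep the contrast as a screen, but it does not justify the label given to what the screen finds.

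**The obvious alternative is not clean either.** At 8/3/11, non-responders against all T3 passers still flags an SU-only marker in 35% or 62% of trials. The power gain for a true resistance marker there is only about 4 points. This also stands: changing the comparison group alone does not remove the mislabelling. The desensitised-only children must be examined separately.

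**Non-responder might mean every child without SU.** Then nobody is left out. But a marker of sustained response would still be called resistance, so the labelling problem remains.

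**The figures are for one uncorrected marker.** Item ii covers many cell subsets, and correction would lower every figure. True; they illustrate direction and rough size only.

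**Stronger readings that the documents do not support.** A reader might infer that non-responders are by definition the children who react at T3. The term is undefined, section 4.3.2.6 sends only children who have completed maintenance to T3, and withdrawn children may be profiled at a visit that lists no challenge (section 4.4.2). A reader might also infer that T3 and T4 blood is drawn after dosing, so that acute reactions contaminate the comparison. Section 4.3.2.8 says only that an optional cannula is a safety precaution "and also allows blood to be collected without further venepuncture"; it does not say when blood is taken.

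**Conclusion.** The point holds as one of specification and labelling. The single named contrast cannot separate failure to desensitise from failure to sustain, and the desensitisation-against-SU part of objective 6 has no named contrast. Under the stated assumptions, a marker of sustained response alone would be called resistance in 40-53% of trials at 1.0 SD and 72-86% at 1.5 SD. The loss of power for a true resistance marker is moderate if SU is near 28% (40% against 57% at 1.0 SD) and small if it is near 50% (53% against 57%). With about 15 completers, power at 1.0 SD is poor under either contrast.

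A reader might go further and conclude that objective 6 cannot be answered. That is too strong: all three groups are sampled, item iii is worded broadly, and the missing comparisons can be added on planned samples. This is an exploratory secondary objective. The primary endpoint and the sample size are unaffected, so it is a cheap improvement and not a flaw in the trial's main conclusion.

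**What to change.** In section 4.3.2.10, items ii and iii:

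1. Define three response groups in the active arm: non-responder, desensitised without SU, and SU. State how children who never reach T3, or who withdraw, are counted.
2. Keep non-responders v SU as a screen.
3. Add non-responders v all T3 passers (resistance) and SU v desensitised without SU (sustained response).
4. Call a marker resistance only if desensitised-without-SU children resemble SU children and not non-responders. Judge this from estimates with confidence intervals, since a non-significant test in so few children does not show similarity.
5. Use the TS sample for signatures said to confer resistance, because they must precede treatment.

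As a separate minor clarification, state that TS, T3 and T4 blood is drawn before the first challenge dose.

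Cost: protocol wording and a little more analysis; no added child, visit or sample. The groups will be small, with as few as 3 desensitised-only children if SU reaches 50%, and the all-passer contrast has less power for a graded marker, which is why the planned contrast is kept. The wording should be settled before response groups are known, so that contrasts are not chosen after seeing the data.

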9.2 Statistical and Analytical Plans

The primary analysis will be performed on an intention to treat basis: all subjects allocated to each arm will be analysed together as representing that treatment arm, irrespective of compliance and whether or not they have completed the prescribed regimen. A secondary

analysis will also be performed on a per protocol basis. Statistical analysis was performed using SAS software version 9.4 for Windows (Cary, NC: SAS Institute Inc.). Statistical significant is set at $p < 0.05$.

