9.2.2 Analysis of Secondary Outcomes

The following secondary analyses will be performed:

- Proportion of subjects who tolerate 4443mg or more of egg protein in the active and control groups, following cessation of all egg intake for 6 weeks (sustained unresponsiveness), using a two-sided Fisher's exact test.
- The incidence of adverse events experienced between active and control groups. Statistical differences will be determined using two-sided Fisher's exact test for proportions; non parametric tests for graded reactions. Logistic regression will be used to assess the association of age, gender, asthma status and prior history of anaphylaxis with incidence of adverse events.
- Completion rates in the active and control groups will be compared using a two-sided Fisher's exact test.
- Change in quality of life assessments before and after OIT, as assessed by FAQL-Q in children, teenagers and their parents – between the active and control groups using two independent sample t test (or Mann-Whitney U test if normality assumption is not tenable). The changes within each group will be assessed using paired t test (or Wilcoxon signed rank test if normality assumption is not tenable).
- Immunological outcome measures pre- and post- of OIT, using paired t test (or Wilcoxon signed rank test if normality assumption is not tenable) within each group.

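### The immune-signature search has no named test, no feature list and no multiplicity rule; applying the plan's p < 0.05 to each cell subset would put the chance of a false signature well above 5%

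*Combined protocol and SAP*

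**What the plan says.** Section 2.3 lists the immune work among the secondary objectives. Objective 5 compares immune cell profiles at baseline and at the end of OIT. Objective 6 is "To identify the mechanistic basis of resistance, desensitisation and SU to OIT". Neither is labelled exploratory.

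Section 4.3.2.10 gives the method. Cytometry is to "determine the differences between non-responders and those with SU to identify immune signatures that confer resistance to OIT", and "Absolute counts of B, T, natural killer and dendritic cell subsets will be characterised". Four lineages are named, but the subsets are neither listed nor counted. Blood "will be concurrently collected (TS, T3 and if applicable, T4"; no time point is named as the main one. Non-responder is not defined. Transcriptomic analysis follows, at a resolution chosen "depending on the immune cell profiling data to identify the pathways responsible for the differences in response to OIT". Cytokine profiling is done only if cytometry points that way.

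On inference, section 9.2 has one general rule: "Statistical significant is set at $p < 0.05". For immunology, section 9.2.2 offers only "Immunological outcome measures pre- and post- of OIT, using paired t test" (or its rank counterpart) within each group. That can serve objective 5. It does not cover non-responders against children with SU, which is a comparison between groups. Nothing in the document mentions adjustment for multiple tests, false discovery control or validation of a signature.

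**The concern.** Objective 6 promises a finding in causal language: features that confer resistance. The only yardstick a reader can apply is p < 0.05, and the number of features to which it may be applied has no limit. A signature could then be reported mainly because many subsets were examined in two very small groups. What is at stake is how objectives 5 and 6 can be interpreted, and what a later study would build on. The efficacy conclusion is not at stake.

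**Working it through.** **Plan's own figure.** The plan states no error rate or number of tests for this search, so there is none to reproduce. The only plan figure used is the sample size, "who will be randomised 2:1 to active (n=22) or control (n=11) groups". It reproduces with an unpooled two-proportion formula (65% v 15%, 2:1, two-sided 0.05, 80% power): 7.57 controls × 3 = 22.7, so 23; 23 / 0.70 = 32.9, so 33.

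**Group sizes (assumed from the plan's rates).**
- Non-responders, taken as not desensitised: 22 × (1 − 0.65) = 7.7, about 8.
- SU, at the roughly 30% in section 6.1: 22 × 0.30 = 6.6, about 7. The 28–50% in section 1.1 would give 6 to 11.
- After the 30% attrition in section 9.1: 8 × 0.7 = 5.6 and 7 × 0.7 = 4.9, about 5 v 5.

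**Number of subsets m (assumed, because not stated).** Shown for 10, 20 and 30.

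**Independent subsets, t test, no true difference.** Chance of at least one p < 0.05 = 1 − 0.95^m.

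| m | Chance |
|---|---|
| 4 | 18.5% |
| 10 | 40.1% |
| 14 | 51.2% |
| 20 | 64.2% |
| 30 | 78.5% |

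**Correlated subsets and rank tests.** Subsets from one blood sample are correlated, which lowers these figures. Exact Mann-Whitney tests lower them further, because in small groups their attained level is below 5% (0.040 at 8 v 7, 0.032 at 5 v 5). Simulation with equicorrelated normal markers, 20 subsets, 8 v 7, one time point:

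| Correlation | t test | Exact rank test |
|---|---|---|
| 0 | about 64% | about 56% |
| 0.3 | about 55% | about 48% |
| 0.5 | about 44% | about 38–40% |

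Simulation error is about one percentage point. The highest value is the independent t-test case and the lowest is the rank test at correlation 0.5. On that basis the ranges are about 26–40% for 10 subsets, 40–64% for 20 and 49–79% for 30. At 5 v 5 with rank tests, 20 subsets give about 48%, 42% and 36% at correlations 0, 0.3 and 0.5.

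**More than one time point.** Non-responders have no T4 visit, so the groups can be compared at TS, at T3 and on the change. With all three tested (t tests, 8 v 7, assumed within-child correlation 0.5), the chance at between-subset correlation 0 / 0.3 / 0.5 is:
- 10 subsets: 74% / 68% / 58%
- 20 subsets: 93% / 88% / 76%
- 30 subsets: 98% / 94% / 85%

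**With Benjamini-Hochberg at 5%.** The chance of any false rejection is about 4–5% at 8 v 7.

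**What that costs in power.** With one true 1.5 SD difference among 20 subsets, power by t test at 8 v 7 falls from about 76% to about 27%. At 5 v 5 the smallest two-sided exact rank p is 2/252 = 0.0079, while a lone feature among 20 must reach 0.05/20 = 0.0025. A single subset could then never pass, and power is below 1%.

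**The case against.** The strongest reply is that the plan never says one subset below 0.05 makes a signature. Section 9.2 sets a generic level and section 9.2.2 lists tests, none of them for this contrast. This stands: the error rates above are conditional on the 5% level being applied to each subset. It does not remove the concern, because no other criterion is offered.

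A reader might infer three stronger things that the documents do not support.
- **That a false signature is more likely than not, or that objective 6 can hardly fail, at 20 subsets.** The count of 20 appears nowhere in the plan. At one time point the chance is below one half with correlation 0.5, and with rank tests once subsets are correlated or groups shrink to 5 v 5.
- **That a false cytometry hit triggers the next assay.** Transcriptomics is planned in any case and only its resolution depends on cytometry. The cytokine step is conditional, but not on a p value or on this contrast.
- **That transcriptome-wide testing would yield some particular large number of false hits.** No feature count is given.

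It is also fair to say that this is small-sample mechanistic work and that adjustment leaves little power. That supports an exploratory label, which the plan lacks. It also argues against using an adjusted threshold to decide whether later assays are run.

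**Conclusion.** The concern holds in a conditional form. The search behind objectives 5 and 6 has no multiplicity rule, and its central comparison has no test, feature list or main time point. If the general p < 0.05 is used subset by subset, the chance of at least one false signature is about 26–40% for 10 subsets, 40–64% for 20 and 49–79% for 30, against a nominal 5%. Testing TS, T3 and change raises it further.

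These figures rest on assumed group sizes of 8 and 7, assumed subset counts, normal markers and correlations from 0 to 0.5. They do not show that a false signature is probable in every plausible setting. The primary Fisher test and the clinical secondary outcomes are untouched. Label: cheap improvement.

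**What to change.** Add one paragraph to section 9.2 before the immune data are examined:

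- Limit the unadjusted p < 0.05 rule to the clinical outcomes.
- Label objectives 5 and 6 exploratory and name the test whose p values will be adjusted, since 9.2.2 gives none for non-responders against SU.
- Within each assay panel (cytometry, transcriptome, cytokines), report Benjamini-Hochberg adjusted p values over all features tested, next to the estimates and intervals, and state how many features were tested.
- Call a feature a signature only if it passes a false discovery rate stated in advance, 5% or 10%.
- Do not make the later assays conditional on this threshold. That is a question of scientific strategy, and with this little power such a gate would often block a real lead.

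The cost is a paragraph and a few lines of code, with no extra children or blood. The downside is that, with about 5 to 8 children per group, few features will pass. Objective 6 may therefore end as hypothesis-generating only.
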